Inducing a false sense of security is perhaps unavoidable with the introduction of any new monitoring modality. During our education sessions with providers, it will be stressed that MEWS++ is an investigational alert and it should not override clinical judgement. We will have two further mechanisms for soliciting clinician feedback and ensuring a false sense of security is not imbued in the staff. First, we will be in close communication with nursing and RRT leadership throughout the pilot, via check-in meetings initially weekly, and then monthly or as needed throughout the study. Second, the RRT team logs details of every RRT visit to a REDCap database. These data are automatically integrated into our analysis pipeline. We match alerts to RRT calls as part of our performance monitoring. If a deterioration occurs that is missed by our algorithm but seen by RRT, will be able to analyze and understand what factors may have contributed to the miss, and if alert fatigue or a false sense of security contributed to the miss.

Description of Procedures Taken to Lessen the Probability or Magnitude of Risks

No additional data will be gathered beyond that of the standard of care for patients, thus limiting risks of the additional information. The research personnel table lists all personnel who may obtain viewing privileges to the collected data.

Provisions for Research Related Harm / Injury

There is no risk of research related to harm or injury as no therapeutic intervention is made based on the results from this study's evaluation. All participant will receive standard of care interventions.

Expected Direct Benefit to Subjects

As a direct benefit from enrolling in this study, we expect the subjects will be more closely monitored for deterioration in clinical condition and will receive more immediate escalation in care when compared to both historical and matched control subjects.

Benefit to Society

We hope that the proposed technology will prove to have a highly sensitive and specificity for predicting individuals who are at risk of clinical deterioration and may require a higher/more intensive level of care. If this does prove to be true, this would be a significant advance to the field of medicine. It would help to reduce death within an inpatient hospital setting.

Provisions to Protect the Privacy Interests of Subjects

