By only allowing only members of the investigational team to access PHI we protect subjects' privacy. All study personnel has completed HIPAA training, which ensures the utmost care is used to handle PHI.

Economic Impact on Subjects

There is no economic burden on the patient.

11. Procedures - Narrative

Description of the Study Design

Patients admitted to 10W and 10E meeting the inclusion and exclusion criteria will undergo a modified RRT evaluation protocol as detailed in Appendix 4: Process Flow. In brief, the patient will be evaluated based on our retrospectively validated machine learning algorithm (MEWS++) designed to improve identification of patients who may need care escalation. Patients on 9W and 9E will be followed but no alerts, interventions or changes from standard of care will be pursued. The study is designed to evaluate the equivalence in the proportion of escalations between the standard of care RRT protocol and our proposed ReSCUE-ME protocol. Patients admitted to 9W and 9E will not undergo any additional monitoring and thus will serve as controls.

Further details of the alerting system are listed below.

- a. Notifications can be suppressed or re-enabled on a per-patient basis. This is a core feature as it is needed to fulfill the opt-out process that we documented in our application's appendices.
- b. Currently there are several automated alerts sent to Vocera. These include ventilator and telemetry alarms, e.g. an alarm if the ECG monitor detects asystole. There is also a simple rules-based Epic BPA for hyperkalemia that sends an alert to the Vocera if a patient's potassium level is high. There is an administrative policy on alarm management that covers these existing alerts - Clinical Alarm Management GPP-242 – link to policy below: <http://policies.mountsinai.org/web/general-policies-and-procedures/policies/-/policy-management/viewPolicy/565852/>.

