Receipt or Transmission of Data	No
Holding Code That Can Be Linked to Identity of Participants	No

Duration Data Will Be Stored

Data are stored in accordance with the data retention policy of the manuscript in which the results will be published. This may vary by publication but is generally 7 years.

Steps That Will Be Taken to Secure the Data During Storage, Use, and Transmission

Only the designated investigator and co-investigators as listed on this form will have access to patient data used in this study and will be the sole arbiters for receipt and transmission of this data. The data will be password protected on Mount Sinai computers. Data are encrypted both at rest (i.e., when stored in the database) and while in motion (i.e., during transit between various components of the alerting system) using industry standard encryption protocols. Data will only be accessed from within the Mount Sinai network to ensure confidentiality, which is also password protected and physical access restricted. Any presentation will separate the presented material from the associated identifiers. All individuals have completed institutionally approved HIPAA training.

Power Analysis/Data Analysis Plan (Including Any Statistical Procedures)

Sample size calculation

Based on the pilot feasibility study, the current true rate of escalation of care in the selected units is ~ 10%. We expect that MEWS++ will identify at least 50% of the escalations, on average ~ 6 hrs before the expected time of deterioration/escalation. It is estimated that RRT and front-line providers collaboratively will be able to prevent ~ 20% of the predicted escalations. We are specifying a non-inferiority or superiority margin of 5%. As a result, the estimated sample size needing to achieve a type 1 error of 5% and power of 95% is 934. based on the rate of escalation ~ 10%, a total of approximately 9340-bed movements will need to be recruited for this study in the MEWS++ group and a total of 18680-bed movements across both groups. We assumed that there is not a significant

difference in the escalation rate between the selected units (10E and 10W) and control units (9E and 9W). Interim evaluations every 6 month will be conducted and if at any point the model meets statistical significance or major flaws identified, a subsequent report will be submitted.

Statistical Analysis:

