At the alert level, the status of ICU escalation, whether a type of medical order or laboratory order is placed, and the total number of medical orders and laboratory orders following each alert were summarized. The descriptive summary of alert level analysis was also performed for the subset of RRT alerts and primary alerts. Confusion matrices were used to analyze the performance of RRT alert versus none alert and any alert (rrt alert or primary alert) versus none alert, individually, in association with actual escalation and actual escalation to ICU within MEWS arm where all patients received MEWS escalation monitoring and provider alerting. In the floor unit level analysis, escalation status, ICU status, alert levels, and the total number alerts were summarized.

Statistical Analysis Plan Summary of Changes

Primary outcome

Analysis was limited to first hospitalization. For patients who had crossover between intervention and control arms, treatment group was determined by initial study arm from the first unit admission. Inverse probability of treatment weight was chosen as the method to account for differences between treatment arms.

Secondary outcomes

The analysis of the secondary outcomes was modified as follows:

Secondary Outcome Number	Secondary Outcome Description	Modification
3	Number of participants requiring respiratory support	This outcome was removed due to too few events. Only 20 respiratory therapy orders were placed across both intervention and control groups.
4	Number of cardiac arrest episodes	This outcome was removed due to too few events. There were no episodes of cardiac arrest.
5	Mortality Rate	This was further clarified to be combined in-hospital and 30-day mortality.
6	Notification Frequency	This outcome was removed. As implemented, the number of alerts generated per patient was capped at 3 per unit admission in both arms.
7	Number of calls	This outcome was removed. It was intended to measure the number of calls to RRT initiated by clinicians independent of the alert system. Low data quality in the separate RRT call tracking system made the data unusable.

Ad-hoc outcomes

The following ad-hoc outcomes were added:

1. Likelihood of ICU escalation within 12 and 24 hours
2. Likelihood of earlier hospital discharge

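### The equivalence objective and the 5% margin that sizes the trial, with its stated 95% power, do not address the roughly 1-point reduction in escalations that the plan expects

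*Combined protocol and SAP*

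**What the plan says.** Four parts of the document bear on the aim of the comparison.

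- **Objective** (section 11, Description of the Study Design): "The study is designed to evaluate the equivalence in the proportion of escalations between the standard of care RRT protocol" and the ReSCUE-ME protocol.
- **Sizing** (section 19, Sample size calculation): "the current true rate of escalation of care in the selected units is ~ 10" percent; "We expect that MEWS++ will identify at least 50% of the escalations"; and "RRT and front-line providers collaboratively will be able to prevent ~ 20% of the predicted escalations". Then: "We are specifying a non-inferiority or superiority margin of 5" percent, with type 1 error 5%, power 95% and a sample size of 934. Dividing by the 10% rate turns this into 9,340 bed movements per group, 18,680 in all. The text does not say whether the margin is absolute or relative, or whether the error rate is one- or two-sided.
- **Expected benefit** (section 10, Expected Direct Benefit to Subjects): subjects "will receive more immediate escalation in care when compared to both historical and matched control subjects". This is a gain in timing, whereas the sample size paragraph counts escalations prevented.
- **Analysis**: the original SAP lists ordinary difference tests. The December 2021 SAP uses propensity-weighted negative binomial and logistic models, giving a count ratio for escalations and an odds ratio for ever being escalated. Neither contains a margin or an equivalence test. The interim rule in section 19 refers to statistical significance.

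The document also states that the final protocol is the same as the original, so the equivalence sentence and the margin still stand.

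**The concern.** The risk section says that the alert is one more notification on top of those the response team already receives, and that none is removed. For an add-on of this kind, similarity to usual care is also what an alert with no effect would produce. An equivalence objective suits a replacement that is cheaper or simpler. It does not suit an addition that is expected to prevent escalations or bring them forward.

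The margin makes this worse. Five points is half of the 10% base rate and five times the reduction that the plan expects. A reader who takes the objective and the 95% power at face value would think the trial well powered for its purpose. That power is for showing that two equal rates lie within 5 points of each other, which says nothing about whether the alert helps.

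**Working it through.** **Inputs** (section 19): control rate 0.10; share of escalations identified 0.50 (given as a minimum); share of those prevented 0.20; margin 0.05, taken as absolute; alpha 0.05; power 0.95; 9,340 bed movements per arm.

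**1. Expected effect.** 0.10 x 0.50 x 0.20 = 0.01, so 10% falls to 9%.

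**2. The plan's own figure.** Two one-sided tests, equal rates, no true difference:

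n per arm = 2p(1-p)(z0.95 + z0.975)² / margin² = 0.18 x (1.645 + 1.960)² / 0.0025 = 936, against 934 stated.

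Non-inferiority at one-sided 2.5% with equal rates uses the same z-values and also gives 936. Other readings give:

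- non-inferiority at one-sided 5%: 780
- equivalence with the 1-point benefit built in: 1,163
- non-inferiority at one-sided 2.5% with that benefit in the favourable direction: 621
- superiority, 10% versus 9%: 22,342 (two-sided) or 18,607 (one-sided)
- a relative 5% margin (0.5 point), equivalence: 93,562

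One-sided superiority for 10% versus 15% comes close at 945, but the text describes no such rise. The stated number therefore fits a calculation with no true difference; the expected benefit was not used. The 936 counts movements per arm. Section 7 treats 934 as a count of escalations, which is how the tenfold larger 9,340 arises.

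**3. Chance of meeting an equivalence objective.** With d the true difference and SE = sqrt[(pC(1-pC) + pT(1-pT))/n], the probability is Φ((0.05-d)/SE - 1.645) - Φ((-0.05-d)/SE + 1.645). For 13% at 9,340: SE = sqrt[(0.09 + 0.1131)/9,340] = 0.00466, and 0.02/0.00466 - 1.645 = 2.64, giving 99.6%. The design effects are assumptions, since the documents give none; 934 effective corresponds to a design effect of 10.

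| True alert-arm rate | 9,340 independent | Design effect 3 | 934 effective |
|---|---|---|---|
| 9% (expected benefit) | >99.9% | >99.9% | 90.1% |
| 10% (no effect) | >99.9% | >99.9% | 95.0% |
| 12% | >99.9% | 98.4% | 66.5% |
| 13% | 99.6% | 79.7% | 38.6% |
| 14% | 67.8% | 33.4% | 16.4% |

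With equal 10% rates at 9,340 per arm, SE = sqrt(0.18/9,340) = 0.0044. An observed difference of up to about 0.05 - 1.645 x 0.0044 = 4.3 points would count as equivalent.

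**4. The other readings of the margin.** Non-inferiority at one-sided 5%, with more escalations as the unfavourable direction: 9% and 10% both pass with over 99.9% probability at 9,340, and with 99.7% and 97.5% at 934. Superiority by 5 points: for a true 1-point reduction, SE = sqrt[(0.09 + 0.0819)/9,340] = 0.0043, and (0.01 - 0.05)/0.0043 - 1.645 is about -11, so the power is essentially zero.

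**5. Power for the expected difference.** At 9,340 per arm, 0.01/0.00429 = 2.33. Two-sided 5%: Φ(2.33 - 1.96) = 64%. One-sided 5%: Φ(2.33 - 1.645) = 75%. The half-width of a 95% interval is 1.96 x 0.0044 = 0.86 points.

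**The case against.** The strongest reply is that no planned analysis tests equivalence. Both SAPs test or estimate differences, and the final one models escalation directly. This stands, and it limits the point. A reader might infer that the trial's results cannot separate benefit, no effect and a rise in escalations, or that a sizeable rise would be reported as equivalent. The documents do not support either: the weighted ratios can show a difference in either direction, and no text sets a rule for claiming equivalence.

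The margin is also not labelled an equivalence margin. Joining it to the equivalence sentence is an interpretation, and the 936 does not settle it, because non-inferiority at one-sided 2.5% gives the same number. This too stands, but none of the three readings makes the objective informative about a 1-point effect.

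A reader might regard a rise to 13% as harm. The documents do not define more escalations as harm, and the primary endpoint has no stated direction. Showing that alerts do not materially change escalation volume could be a legitimate aim, but the plan does not present it as the reason for the margin. The figures for a rise also depend strongly on the effective sample size, as the table shows.

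Finally, in the SAP's Summary of Changes, "treatment group was determined by initial study arm from the first unit admission". A reader might infer that this pulls the arms together in favour of the claim. That would matter only in an equivalence test, which is not planned. For the difference analyses, such dilution is conservative, so it is not part of the error.

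**Conclusion.** The point holds as a mismatch between the stated objective, margin and power on one side and the expected benefit and the planned analyses on the other. The 95% power belongs to a comparison with no true difference. For the expected 10% to 9%, the power at 9,340 per arm is about 64% two-sided, and 95% would need 22,342 per arm. This rests on an absolute margin, a 10% control rate, the minimum 50% identification figure and independent movements. Correlation within patients and units, and the final SAP's restriction to first hospitalizations, would lower the power by an amount the documents do not allow one to compute. The finding concerns escalations only. The primary endpoint also includes response-team-initiated therapy, for which the plan gives no rate.

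**What to change.** 1. In section 11, replace the equivalence sentence with wording such as: *The study will estimate and test the difference in escalation of care between 10E/10W and 9E/9W, with a two-sided 95% confidence interval; a non-significant difference will not be taken as evidence of equivalence.*
2. In section 19, remove the 5% margin. Restate the power for 10% versus 9% as about 64% (two-sided 5%) or 75% (one-sided 5%) at 9,340 independent movements per arm, and say that it is lower with correlation within patients and units and with first hospitalizations only.
3. Reconcile sections 10 and 19 on whether fewer or earlier escalations is the expected benefit, and state which direction of the primary endpoint counts as success.

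The final SAP already reports event counts, so the change should be dated and disclosed as made after data had been seen. It brings the objective into line with the models already specified and needs no new data. The cost is document wording, a less favourable stated power and a possibly inconclusive result. A supplementary analysis of patients who moved between arms is optional.

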Description of the Source Records that Will Be Used to Collect Data About Subjects

For each patient, real-time data from the EHR, the admitting system (Cerner ADT), the ECG (MUSE), and laboratory information systems (SCC) will be ingested by the ReSCUE-ME engine and used to generate a prediction score. Additional information provided by the RRT team on the result of the RRT intervention will be extracted from REDCap. These values as specified in Appendix 3 will be processed through the ReSCUE-ME data streaming engine to generate a MEWS++ score for patients who have not been excluded or withdrawn from the study. If an individual withdraws participation from the study, all data pertaining to this patient's current visit will be removed from

ReSCUE-ME. Clinical documents may also be assessed for the purpose of further clarification of events during the RRT intervention.

Description of Data that Will Be Collected Including Long-Term Follow-Up

The data that will be collected during this study include vitals, electrocardiogram, laboratory data, clinical evaluations, and patient demographics from ADT, Epic, MUSE, and Laboratory Information System. A detailed list is provided in Appendix 3. At this time we do not plan on conducting long-term follow-up upon the discharge of the patient from their current hospital visit.

Research Requires HIV Testing No

12. Procedures - Genetic Testing

Genetic Testing Will Be Performed No

Guidance and Policies > Future Use Data Sharing and Genetic Research

13. Procedures - Details**Surveys or Interviews** Yes**Type of Instruments Being Used** Created By Research Team**Description of Instruments Created By Research Team**

A REDCap survey will be created to understand the impact of the alerts on the RRT team. This clinician survey has not yet been developed. We will not do this piece of the research until the survey has been approved by the IRB and the protocol modified appropriately and also approved.

Audio / Photo / Video Recording No**Deception** No**Results of the Study Will Be Shared** No
with Subjects or Others

14. Procedures - Instruments**Instruments Created By Research Team**

Type	REDCap RRT survey
Name	REDCap RRT survey
Upload	REDCap RRT Survey Placeholder.docx

15. Procedures - Compensation

Compensation for Participation No

16. Consent - Waiver of Informed Consent

Requesting Waiver For

At the request of the IRB, the principal investigator developed the following opt out process in cases where patients did not want to participate:

Opt-Out Process for ReSCUE-ME

1. Every patient will receive at least one printed copy of the "Waiver Information Sheet" letter at various entry points into the hospital unit:
 - a. The 9W, 9E, 10W, and 10E business associate will insert a print out of this waiver into their "welcome packet" (a packet of information given to all patients entering any hospital unit) as part of the current standard operating procedure.
2. We will offer to distribute this letter to every hospitalist through Mount Sinai Medicine Department's Division of Hospital Medicine.
4. The opt-out letter will be in English and Spanish.

Educating Nursing and Physicians about the Opt-Out Process

1. An educational conference will be partially devoted to the subject of introducing the study and explaining the scientific background and methods of the research.
 - a. Medicine Department's Division of Hospital Medicine
 - b. The Mount Sinai's Institute for Critical Care Medicine
 - c. Nursing Teams on the participating units.
2. All members of the hospitalist and rapid response care team (attending, residents, and nursing) will be given a script that will be posted on the departmental intranet to give patients information regarding the study.
3. All members of the hospitalist care team and business associates on the participating units will be given instruction as to the procedure for withdrawing patients from the study.

Instructions for Hospitalist Care Team:

1. If the patient has no questions regarding the ReSCUE-ME Study, then proceed as usual.
2. If the patient has questions regarding the ReSCUE-ME Study that you cannot answer, please page one of the investigators listed on the Clinical Data Science group's intranet link for the study. If you cannot obtain an answer quickly for the patient, offer the patient the option of withdrawing from the research.
3. If the patient spontaneously, or after having had questions answered, wishes to withdraw from the research, the provider should submit a request to the <http://cds.mountsinai.org/ReSCUEMe> website.

Type of Waiver

Waiver of Consent

How the Research Involves No More Than Minimal Risks to Participants

All participant subjects will receive standard of care at all times. The MEWS++ alerts will simply inform the clinicians that a patient may be in danger of clinical deterioration, without providing any suggestions on the best course of care. The most appropriate intervention will be determined by the treating clinician.

How the Waiver / Alteration Will Not Adversely Affect the Rights and Welfare of Participants

There will be no alteration to the standard of therapeutic care in the proposed study in either the interventional or non-interventional group. As a result, we don't anticipate any detrimental changes to the welfare of the patient based on the MEWS++ and MEWS scoring and the potential for increased monitoring. Conversely, we expect that ReSCUE-ME will improve patient welfare by improving care.

Why It Is Not Practical To Conduct this Research Without a Waiver or Alteration of Informed Consent

The number of potential patients that need to have consented means that obtaining consent is neither feasible nor practical as it would lead to an overwhelming burden on staffing resources.

Plans for Providing Participants with Additional Pertinent Information After Participation Where Appropriate

The care providers will be contacted during this enrollment period for any clinically relevant information that may arise during analysis, though acting on such information is at the discretion of the care provider. This contact may be through grand rounds presentations, in-service training, email distribution, or other means.

17. Data - Collection

Health Related Information Will Be Viewed, Recorded, or Generated Yes

Description of Health Information That Will Be Viewed, Recorded, or Generated

The artificial intelligence algorithm will process and analyze data obtained from the EHR and other systems as previously described. The Data Collection Sheet contains the exact list of variables. The algorithm generates a MEWS++ score that is viewable through the EHR by the care provider team.

Non-Health Related Information Will Be Viewed or Recorded No

HIV / AIDS Related Information Will Be Viewed or Recorded No

Data That Will Be Viewed, Recorded, or Generated Contains ANY of the Following Directly Identifiable Information Yes

Will Be Viewed Medical Record Number

Will Be Recorded Medical Record Number

Data Collection Sheet DataElements.xlsx

A Data Collection Sheet is required if you are either performing a retrospective review, or your study meets the category of exempt 4 research, or your study meets the category of expedited 5 research. Please upload it here.

Data Collection Source(s) Medical Chart (Paper or Electronic), Data Warehouse

18. Data - HIPAA

Obtaining HIPAA Authorization	No
Requesting Waiver or Alteration	Waiver
Research Could Be Practicably Conducted Without Access to and Use of Protected Health Information (PHI)	No

Explanation Why Research Could Not Be Practicably Conducted Without Access to and Use of PHI

In order for a MEWS++ alert to be of value, the provider needs to know the identity of the patient for whom the alert was generated. Thus the alerting system needs to know the identity of the patient as well.

Explanation Why Research Could Not Be Practicably Conducted Without a Waiver or Alteration of Authorization

It is neither practical nor feasible to consent over 18,000 individual patients. Additional details on why we are requesting a waiver can be found under the "Consent" section of this IRB application.

How PHI Will Be Protected from Improper Use or Disclosure

All PHI will be stored in secure, password protected servers that can only be accessed by authorized members of the study team. All study personnel have completed HIPAA and human subjects research training, which ensures utmost care is used to handle PHI.

PHI Will Be Destroyed at the Earliest Opportunity Consistent with the Research	Yes
--	-----

When and How PHI Will Be Destroyed

Data are stored in accordance with the data retention policy of the manuscript in which the results will be published. This may vary by publication but is generally 7 years. Data will be destroyed by overwriting the disk sectors used to store the data with 0s.

PHI Will Be Shared	No
--------------------	----

PI must attest to the following.

**** I assure that the protected health information (PHI) will not be disclosed to any other person or entity not listed on this form except where required by law or for the authorized oversight of this research project. If at any time I want to reuse this PHI for other purposes or disclose it to other individuals or entities I will seek approval from the IRB.***

19. Data - Storage

Location Where Data Will Be Stored

Secure servers within the hospital data center.

How will the data be stored? Other

Specify How Data Will Be Stored

